8.8.9 Serum numbering

- 1) Test tube numbering for anti-SARS-CoV-2 neutralizing antibodies: Study ID-visit number-1
- 2) Test tube numbering for anti-SARS-CoV-2 RBD protein IgG antibodies (ELISA) and serum IgA: Study ID-visit number-2
- 3) Test tube numbering for anti-recombinant replication-defective human type 5 adenovirus neutralizing antibodies: Study ID-visit number-3
- 4) Test tube numbering for saliva samples: Study ID-visit number
- 5) Test tube numbering for antigen-specific CD4⁺ T cell and CD8⁺ T cell responses: Study ID- visit number-P
- 6) Test tube numbering for backup serum samples: Study ID-visit number-3 (except blood before immunization) and study number-visit number-4.

8.8.10 Storage and transportation of samples

Storage and transportation of samples will be performed using unified operating standards. The samples should be stored at -20°C or below and delivered to the testing laboratory in time.

8.9 On-Site Workflow

8.9.1 Overview of visit procedures

From the beginning of the screening prior to the enrollment to the end of the study, the subjects will complete all the study content in 5 or 6 visits. The specific time, time window, and content for each visit are detailed in 8.9-1.

Table 8.9-1. Visit procedures

Visit point	V1	V2	V3	V4	V5
Visit time	D-7-D0	D14	D28	Month 3	Month 6
Time window	/	± 3 days	± 5 days	± 15 days	± 15 days
Informed consent	•				
Registration/identity verification	•	•	•	•	•
Physical examination (blood pressure, height, weight, body temperature)	•				
Urine pregnancy (female of childbearing potential)	•				
Medical history inquiry and eligibility screening	•				
Randomization number assignment ^a	•				
Immunogenicity blood sampling ^a	10 mL	10 mL	10 mL	10 mL	10 mL
Cellular immunity blood sampling ^b	15 mL	15 mL			
Saliva sampling ^c	2 mL	2 mL	2 mL	2 mL	2 mL
Immunization ^d	•				
Dispensation of diary card (0–14 days)	•				
Return of diary card (0–14 days)		•			
Dispensation of diary card (after 14 days)					
Return of diary card (after 14 days)			•		
Safety observations ^e	•	•	•		
SAE observation and reporting ^f	•	•	•	•	•

- Immunogenicity group only;
- Subjects in the immunogenicity group recruited from Jiangsu CDC who are included in cellular immunity group only;
- Immunogenicity group only;
- If the investigator believes the health status of the subject on the day of vaccination is temporarily unsuitable for vaccination, the dose may be delayed up to 1 week;
- All adverse events within 0–28 days after immunization should be observed and documented, regardless of whether related to the vaccine;
- The investigator should fill out the "Serious Adverse Event Report Form" and complete the initial report within 24 h of learning of an SAE and complete the final report at the end of the event. Except for subjects in the immunogenicity subgroup, all subjects should complete V4–V5 via telephone

Table 8.9-2. Sample collection schedule at clinical trial visits

Visit	V1	V2	V3	V4	V5
Visit time	D0	D14	D28	Month 3	Month 6
Immunogenicity [#]	10 mL	10 mL	10 mL	10 mL	10 mL
Saliva [#]	2 mL	2 mL	2 mL	2 mL	2 mL
Cellular immunity [@]	15 mL	15 mL			

Note: # Immunogenicity group only

@ Subjects in the Jiangsu CDC who are included in cellular immunity group only

8.9.2 Grouping and assignment of on-site personnel

Table 8.9-3. Grouping and assignment of on-site personnel

Serial no.	Group	Responsibility	Visit
1)	Informed consent	Obtain informed consent from subjects	V1
2)	Registration	Perform registration and identity verification	V1–V5
3)	Physical examination	Perform general physical examination prior to enrollment	V1
4)	Urine test	Collect urine for urine pregnancy test	V1
5)	Screening	Conduct inquiry in accordance with the inclusion and exclusion criteria and complete screening forms	V1
6)	Study number assignment	Assign randomization numbers	V1
8)	Immunogenicity blood sampling	Collect 10.0 mL of venous blood	V1–V5
9)	Saliva sampling	Collect 2.0 mL of saliva	V1–V5
10)	Cellular immunity blood sampling	Collect 15.0 mL of venous blood	V1, V2
9)	Vaccination	Perform vaccination according to the procedure and route	V1
10)	On-site observation	Observe subjects for at least 30 min after vaccination	V1
11)	Diary card collection	Collect diary cards and review the format and accuracy of completed diary cards	V2, V3

8.9.3 Site management

[figure not shown]
Table 8.9-4. Grouping and assignment for site management

Serial no.	Group	Responsibility	Visit
1)	Medical guide	1) Maintain on-site order; 2) If necessary, lead subject to each testing group to complete all tests.	V1–V5
2)	Serum separation and management	1) Receive blood samples delivered to the site and fill in the handover form; 2) Isolate serum and aliquot into EP tubes; 3) Store and regularly transport biological specimens; 4) Record the type, quantity, and ID numbers of transported specimens.	V1–V5
3)	Saliva management	1) Receive saliva samples delivered to the site and fill in the handover form; 2) Saliva sample treatment for preservation; 3) Store and regularly transport saliva samples; 4) Record the type, quantity, and ID numbers of transported specimens.	V1–V5
4)	Vaccine management	1) Receive and store vaccines; 2) Record the cold chain temperature; 3) Fill in vaccine issuance and recovery records; 4) Reconcile vaccine quantities at time of locking.	V1
5)	Safety observation	1) Routine safety follow-up; 2) Investigate serious adverse events; 3) Report serious adverse events in a timely manner;	V1–V5
6)	Document management	1) Collect and manage information onsite; 2) Process records; 3) Archive files.	V1–V5
7)	Logistic support	1) Ensure materials meeting requirements; 2) Ensure vehicles meeting requirements.	V1–V5
8)	Emergency care	1) Handle safety incidents and emergencies which require professional ambulance personnel to be onsite; 2) In the event of serious cases, send to the hospital immediately.	V1
9)	Quality control	1) Perform check prior to study initiation; 2) Perform check in one week after subject enrollment; 3) Perform periodic checks during the study; 4) Perform checks at time of site-closing.	V1–V5

8.10 Data Management

In this study, Electronic Data Capture (EDC) system is used for the collection and management of study data, and the complete records of modification are retained by the system to ensure the traceability of the clinical trial data; data collection, entry, cleaning, consistency verification, database lock, and other tasks are completed in accordance with the Technical Guidelines for Data Management in Clinical Trials. The data management process should meet GCP regulations to ensure the authenticity, integrity, and accuracy of the clinical trial data. The main process of data management is shown below. See Data Management Plan (DMP) for additional details.

8.10.1 Data management work flow chart

8.10.2 Roles and responsibilities in data collection

Role	Abbreviations	Responsibility
Clinical data associate	CRC	1. Enter data; 2. Answer queries;
Assistant investigator	Sub-I	1. Enter data; 2. Answer queries;
Principal Investigator	PI	1. Enter data; 2. Answer queries; 3. Approve for confirmation;
Clinical research associate	CRA	1. Verify the consistency of source files 2. Issue queries; 3. Close queries;
Project manager	PM	1. Read only;
Data management	DM	1. Issue queries; 2. Close queries; 3. Freeze/thaw data; 4. Lock data;
Medical coder	Coder	1. Encode; 2. Issue queries.

8.10.3 Design and establishment of database

The database designer establishes the project database (eCRF) in accordance with the CDISC criteria as far as possible.

After the database is established and tested, the authorized persons of the roles, e.g., PI, Sub-I, CRC, PM, CRA, and DM, are trained prior to the formal online application.

The data manager writes the Data Management Plan (DMP), which shall be finalized before the screening of the first subject.

8.10.4 Data entry

The investigators or personnel authorized by the investigators will complete the data entry on-line in a timely manner after the visit.

The investigator must approve for confirmation of the data in eCRF, to demonstrate that the data recorded in the eCRF are true. After completion of data entry, any change to the data must be indicated with comments and will be recorded automatically in the system.

8.10.5 Monitoring of data records

The CRA shall conduct monitoring of data records entered into the EDC on a regular or irregular basis so as to ensure that all recorded data are consistent with the original documents. In the event of inconsistencies, the CRA should send the queries to the investigators in the corresponding section of the EDC system. The investigators should verify the raw data and update the recorded contents until all inconsistencies are resolved in the EDC system. Before locking the database, the monitor should verify the raw data of the subjects carefully and the necessary signatures of the investigators.

8.10.6 Data verification

The data manager conducts query management for the trial data in accordance with the data verification plan (DVP).

When the data is entered into the EDC system, the system automatically verifies any illogical data and issues a query; such a query will be reviewed and answered by the investigator or an authorized person. When updated data renders the logical verification invalid, the query will be closed automatically; DM can review an automatically closed query. If the problem is not solved, then DM can manually add a query and communicate with the study site until the problem is solved.

In addition to automatic verification by the system, the queries can be manually added in the EDC system when the investigator is required to clarify/verify/confirm queries found via SAS programming or manual verification by the data manager.

Before locking the database, the data manager shall ensure that all queries have been cleaned up, and that the investigator has completed the electronic signatures in the EDC system. This is to ensure the integrity and accuracy of the data of patients.

8.10.7 Medical coding

Medical coders conduct medical coding. Medical coding is performed on unsolicited AEs. AEs are encoded in accordance with MedDRA (version 21.1 or higher).

During coding, DM can send queries to the investigators on-line in a real-time manner for coding failure due to improper, inaccurate, or vague medical terminology.

Medical review of medical coding is required before locking the database.

8.10.8 Database locking

The database locking list shall be completed. According to the procedures for database locking, written approval for database locking shall be signed by the data manager, data analysts, representatives of clinical research associates, representatives of investigators, etc., and the data manager will export it to the database in a specified format, and deliver it to data analysts for statistical analysis. After locking the database, if there is definite evidence warranting unlocking, the investigators and related personnel shall sign the unlocking document.

8.10.9 External data management

The immunogenicity data is managed as external data. The requirements on data transmission are shown in the "External Data Transmission Protocol". For data management, external data is subjected to review and consistency verification.

8.10.10 eCRF archiving

After the end of the trial, the eCRF of each patient is exported to PDF for electronic archiving, and is saved into a compact disc and stored in the clinical trial institution.

8.11 Statistical Analysis

8.11.1 Statistical analysis plan

A statistics team (third-party) should be entrusted to carry out statistical analysis and participate in the whole process, from study design, study implementation to analysis and summary. After the trial protocol has been completed and approved by the Ethics Committee, the investigator and statistics team should coordinate the establishment of the database and formulation of statistical analysis plan, before submitting them to the principal investigator, biostatistician, and data manager for review and approval, in order to determine the following: selection of analysis dataset, statistical methods, etc.

8.11.2 Study hypotheses

This study will test a superiority hypothesis. The immunogenicity of 1 booster dose of Ad5 (adenovirus type 5 vector) vaccine for inhalation is non-inferior to that of 1 intramuscular injection of inactivated COVID-19 vaccine.

The superiority test will be carried out with the following hypothesis:

$$H_0 \text{ (null hypothesis): } T/C \leq 1$$

$$H_1 \text{ (alternative hypothesis): } T/C > 1$$

Superiority will be established when the lower limit of the one-sided 97.5% confidence interval of the GMT ratio ($\text{GMT}_{1 \text{ dose of inhalation}}/\text{GMT}_{1 \text{ dose of ICV}}$) of anti-SARS-CoV-2 neutralizing antibodies is greater than 1.

Testing strategy: When superiority is established in the overall population, superiority will also be tested in different age groups (18-59 years old, ≥ 60 years old). Age-stratified results will be used as supportive data. No adjustments will be made to the α .

8.11.3 Selection of analysis sets

Safety set (SS): All randomized subjects who receive the immunization will be included in the safety evaluation. Data in violation of the protocol were not rejected.

Immunogenicity evaluation datasets:

Full analysis set (FAS): FAS included an ideal subject population determined by the intention-to-treat (ITT) principles. All subjects enrolled and vaccinated were included in the FAS, whether or not they had positive baseline antibody levels or major deviation from the protocol.

Per protocol set (PPS): PPS is a subset of FAS; the subjects in this dataset are more compliant with the protocol, have no major protocol violations during the study, and meet all eligibility criteria.

PPS will be used as the primary analysis dataset for immunogenicity analysis in this trial. However, FAS will be analyzed as well. Any inconsistencies between the FAS and PPS results will be discussed in the report.

8.11.4 Data statistical method

Unless otherwise specified, the two-sided testing with $\alpha = 0.05$ and the two-sided 95% confidence interval are used for all statistical tests. Continuous variables are summarized with descriptive statistics, including number of subjects, mean, median, standard deviation, maximum, and minimum. Categorical parameters are described with the number and percentage of subjects in each category.

The statistical analysis will be further described in the Statistical Analysis Plan (SAP) which will be finalized before database locking.

8.11.4.1 Demographics and baseline characteristics

Demographics and baseline characteristics of each group and in total are summarized with descriptive statistics.

Demographics include: enrollment and visit completion (screening failure, protocol violation); the number of subjects from each group in each dataset, and the distribution of age and gender.

Baseline characteristics include: antibody distribution of each immunogenicity evaluation before immunization by group and in total.

8.11.4.2 Safety analysis

AEs are encoded using MedDRA. The analysis of AEs will be based on the treatment-emergent adverse events (TEAEs) after vaccination. A TEAE is defined as an AE that occurs during vaccination or worsens during vaccination compared with the state before vaccination. The incidence of AEs will be summarized by System Organ Class (SOC) and Preferred Term (PT). SAEs and AEs leading to study discontinuation will be similarly summarized and tabulated.

8.11.4.2.1 Incidence of adverse reactions within 30 min post-vaccination

The number of subjects, number of events, and percentage of adverse reactions occurring within 30 min post-vaccination in each group will be summarized. The number of subjects, number of events, and percentages of adverse reactions/events occurring within 30 min post-vaccination in each group by severity and symptoms will be summarized. The inter-group comparison is performed using chi-square test or Fisher's exact test.

8.11.4.2.2 Incidence of adverse reactions within 0–14 days post-vaccination

The number of subjects, number of events, and percentage of adverse reactions occurring within 0–14 days post-vaccination in each group will be summarized. The number of subjects, number of events, and percentage of adverse reactions occurring within 0–14 days post-vaccination in each group will be summarized by severity and symptom. The inter-group comparison is performed using chi-square test or Fisher's exact test.

8.11.4.2.3 Incidence of adverse events/adverse reactions within 0–28 days post-vaccination

The number of subjects, number of events, and percentage of adverse reactions/adverse events occurring within 0–28 days post-vaccination in each group will be summarized. The number of subjects, number of events, and percentage of adverse reactions/adverse events occurring within 0–28 days post-vaccination in each group will be summarized by severity and symptom. The inter- group comparison is performed using chi-square test or Fisher's exact test.

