Group	Vaccine/Dose	Study Center	Sample Size (subject)	Total (subject)															
Safety Group	Ad5-nCoV-IH 1.0×10^{10} VP (0.1 mL)	Jiangsu CDC	2500	10000															
		Chongqing CDC	1500																
		Shandong CDC	1500																
		Hunan CDC	1500																
		Anhui CDC	1500																

		Yunnan CDC	1500	
Immunogenicity Group	Ad5-nCoV-IH 1.0 × 10 ¹⁰ VP (0.1 mL) or ICV (0.5 mL)	Jiangsu CDC	120	420
		Chongqing CDC	60	
		Shandong CDC	60	
		Hunan CDC	60	
		Anhui CDC	60	
		Yunnan CDC	60	
Notes:				

 1. Recruited subjects must have completed prime immunization with 2 doses of inactivated vaccine. 2. The first 60 subjects (120 subjects for Jiangsu CDC) from a single site of each center will be included in the immunogenicity group. 3. The cellular immunity group will consist of the first 60 subjects in the immunogenicity group of a single site managed by Jiangsu CDC, who will undergo ICS testing on Day 0 and 14. 				
Randomization:				

The 420 subjects in the immunogenicity group will be randomized to receive a booster dose of Ad5-nCoV-IH or ICV in a 1:1 ratio. Authorized investigators may assign each enrolled subject a study ID via the IWRS system. The investigators responsible for managing the vaccines will use the investigational vaccine that corresponds to the study ID and group allocation information.
				
Study plan:				

This study plans to enroll 10,420 subjects aged 18 years and old. Subjects ≥ 60 years should account for ≥ 30% of the total population. Subjects must have completed prime immunization with 2 doses of inactivated vaccine. The booster immunization must be ≥ 6 months from the second dose. The safety group will include approximately 10,000 subjects, who will receive a booster dose of Ad5-nCoV-IH to determine the safety of the vaccine.
				

The immunogenicity group will include 420 subjects, and subjects ≥ 60 years should account for ≥ 30% of the population. Eligible subjects who passed consultation and screening and provided informed consent will be randomized in a 1:1 ratio to receive a booster dose of either ICV or Ad5-nCoV-IH. Except for the Jiangsu CDC, the first 60 subjects from a single site of each of the other 5 centers will be included in the immunogenicity group. The first 120 subjects from a single site of the Jiangsu CDC will be included in the immunogenicity group, and the first 60 of these subjects will be included in the cellular immunity group.
				

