6. STUDY DESIGN

Study design:

Multi-center, open-label clinical study, with a randomized, controlled immunogenicity group.

Randomization:

A total of 420 subjects in the immunogenicity group will be randomized in a 1:1 ratio to receive a booster dose of Ad5-nCoV-IH or ICV. Authorized investigators may assign each enrolled subject a study ID via the IWRS system. The investigators responsible for managing the vaccines will use the investigational vaccine that corresponds to the study ID and group allocation information.

Study design:

This study intends to enroll 10420 subjects aged 18 years and above, of which the population aged 60 years and above accounts for approximately $\geq 30\%$. This study includes a safety group and an immunogenicity group. The immunogenicity group also includes a cellular immunity group.

The immunogenicity group will include 420 subjects, and subjects ≥ 60 years should account for $\geq 30\%$ of the population. Eligible subjects who passed consultation and screening and provided informed consent will be randomized in a 1:1 ratio to receive a booster dose of either ICV or Ad5- nCoV-IH. Except for the Jiangsu CDC, the first 60 subjects from a single site of each of the other 5 centers will be included in the immunogenicity group. The first 120 subjects from a single site of the Jiangsu CDC will be included in the immunogenicity group, and the first 60 of these subjects will be included in the cellular immunity group.

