8.11.4.2.4 SAEs within 6 months post-vaccination

The number of subjects, number of events, and percentage of SAEs occurring within 6 months post-vaccination in each group will be summarized. The number of subjects, number of events, and percentage of SAEs occurring within 6 months post-vaccination in each group will be summarized by severity and symptom. The inter-group comparison is performed using chi-square test or Fisher's exact test.

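### The safety-set definition, the randomization text and the between-group safety tests do not fit together: one reading drops the 10,000-subject safety group, the other gives confounded vaccine comparisons

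*Protocol*

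**What the plan says.** **Who is randomized.** Section 6 describes an open-label study in which only the immunogenicity group is randomized: 420 subjects, 1:1 to Ad5-nCoV-IH or ICV. They are the earliest enrolled at one site per center. Outside Jiangsu, "the first 60 subjects from a single site of each of the other 5 centers will be included in the immunogenicity group"; at Jiangsu it is the first 120. Section 8.5 and footnote a of Table 8.9-1 give randomization numbers to the immunogenicity group only. Section 6.3.2 instead has every subject receive one before vaccination.

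**The safety group.** The synopsis states: "The safety group will include approximately 10,000 subjects, who will receive a booster dose of Ad5-nCoV-IH to determine the safety of the vaccine". This group has no ICV control. Section 6.2 rests the safety sample size on it.

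**The safety set.** Section 8.11.3 reads: "All randomized subjects who receive the immunization will be included in the safety evaluation".

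**The tests.** Sections 8.11.4.2.1 to 8.11.4.2.4 cover reactions within 30 minutes, 0–14 days, 0–28 days (the primary safety endpoint) and SAEs to 6 months. Each summarizes by group and prescribes an unadjusted comparison. For the primary safety endpoint, section 8.11.4.2.3 has "group comparison is performed using chi-square test", with Fisher's exact test as the alternative; the 0–14 day section says likewise: "The inter-group comparison is performed using chi-square test or Fisher's exact test". None of them names the groups. Most headings in the immunogenicity section 8.11.4.3 do name the immunogenicity group.

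**The concern.** A reader cannot tell from these sections who is in the safety analysis or what is being compared, and the candidate readings lead to very different analyses.

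If randomized means the 420, the primary safety endpoint is estimated without the subjects who were enrolled to measure safety. If everyone vaccinated is included and the tests are run by vaccine, nearly all of one side is non-randomized. Those subjects come from other vaccination sites or were enrolled after the randomized block at the same site, and they give no blood or saliva. After day 28 they may be followed by telephone at months 3 and 6, whereas the randomized subjects attend in person, which bears on SAE ascertainment. A p-value from an unadjusted test on those data cannot separate vaccine from site, calendar time or case mix.

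**Working it through.** **Inputs from the protocol.** Safety group 10,000 (2,500 + 5 × 1,500); immunogenicity group 420 (120 + 5 × 60), split 1:1; two-sided α of 0.05 for general tests (8.11.4); safety power of at least 85% to see one case at 0.02% incidence (6.2).

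**The protocol's own figure.** 1 − (1 − 0.0002)^10,000 = 0.865, which agrees with at least 85%. The safety sample size therefore assumes that the 10,000 are analysed.

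**Reading A: section 8.11.3 literally, with 6 and 8.5.** The safety set is 420 subjects, of whom 210 received Ad5-nCoV-IH. The chance of seeing one such case becomes 1 − (1 − 0.0002)^210 = 0.041, about 4% instead of 86%. The vaccine comparison is sound (210 vs 210), but the safety objective is lost.

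**Reading B: section 8.11.3 with 6.3.2.** All 10,420 are in the safety set.
- Ad5-nCoV-IH: 10,000 + 210 = 10,210. ICV: 210.
- Non-randomized share of the Ad5-nCoV-IH side: 10,000 / 10,210 = 97.9%.

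**What a shift in the non-randomized group does under reading B.** These rates are assumptions for illustration: the vaccines do not differ, and the adverse-reaction rate is 20% in both randomized arms. Let the safety-group rate be p. The pooled Ad5-nCoV-IH rate is (10,000p + 210 × 0.20) / 10,210. The pooled two-proportion test rejects when the difference exceeds 1.96 × SE0.

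For p = 0.16:
- Ad5-nCoV-IH rate: (1,600 + 42) / 10,210 = 0.1608; difference from ICV 0.0392.
- Overall rate: 0.1616. SE0 = √[0.1616 × 0.8384 × (1/10,210 + 1/210)] = 0.0257.
- True SE = √[0.1608 × 0.8392/10,210 + 0.20 × 0.80/210] = 0.0278.
- Rejection ≈ Φ[(0.0392 − 1.96 × 0.0257) / 0.0278] ≈ 0.34; the opposite tail is negligible.

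Simulation gives the same pattern:

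| Safety-group rate | Rejection at nominal 5% |
|---|---|
| 20% | 5% |
| 18% | 12% |
| 16% | 34% |
| 15% | 49% |
| 22% | 9–10% |
| 25% | 36–37% |

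The bias works in both directions, and it vanishes if the safety group has the same rate as the randomized subjects.

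**Precision given up by restricting to the randomized subjects (20% rate).**
- 10,210 vs 210: √[0.16 × (1/10,210 + 1/210)] = 0.0279.
- 210 vs 210: √[0.16 × 2/210] = 0.0390.

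**The case against.** The strongest objection is section 8.11.3 itself. Read with sections 6 and 8.5 it already gives 210 vs 210, a randomized comparison. A reader might infer that the protocol plans to test 10,210 against 210 and to present the result as randomized. The document does not support that: no section states this comparison, and none says the safety tests are to be read as randomized. The groups could also be the two labels in Table 1 (safety and immunogenicity), or three groups. This part of the objection stands. It does not rescue the text, because the literal reading loses the safety group.

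Several further points limit the size of the concern.
- **No formal decision rests on these p-values.** The only hypothesis (8.11.2) concerns neutralizing antibody, the suspension criteria (6.5) use no between-group test, and the synopsis safety objective names only the inhaled vaccine. Section 5.1, however, names both vaccines.
- **Ascertainment is alike to day 28.** Diary cards, the 30-minute observation and the day 14 and 28 interviews apply to everyone, so telephone follow-up bears on the 6-month SAEs and not on the primary safety endpoint.
- **Age evidence is modest.** A reader might cite the fall from 44% to 14% between age groups in section 3.4.1, but that is a single intramuscular dose, which neither arm receives here. The single medium inhaled dose shows 10% and 4%. On that 6-point gap, a 2-point shift needs the share aged 60 or over to differ by 2/6, or 33 percentage points. The same 30% minimum for that age group applies to the whole study and to the immunogenicity group.
- **The SAP may define comparison groups.** That is normal SAP content. But the protocol itself fixes the safety set and the tests, so a SAP that settled the matter would have to depart from 8.11.3 or restrict 8.11.4.2.

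**Conclusion.** The inconsistency is real and should be corrected. Sections 8.11.3, 6.3.2, 8.5 and 8.11.4.2.1 to 8.11.4.2.4 cannot all be followed while serving the stated safety objective. Under one reading the safety set is 420 subjects and the 10,000 are excluded. Under the other, tests by vaccine have a comparison side that is 98% non-randomized.

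The counts follow directly from the protocol. The rejection rates do not: they depend on assumed shifts in the safety-group rate, for which the document gives no estimate, and they show sensitivity rather than an expected error rate. It is a matter of which reading the protocol permits, not of a confounded test that it demonstrably plans.

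**What to change.** - **8.11.3:** define the safety set as all vaccinated subjects, whether or not randomized.
- **6.3.2 and 8.5:** reconcile them, so that randomization numbers belong to the immunogenicity group and safety-group subjects carry a study number that does not imply randomization.
- **8.11.4.2.1 to 8.11.4.2.4:** confine Ad5-nCoV-IH versus ICV tests, and risk differences with 95% CIs, to the randomized immunogenicity subjects (about 210 vs 210).
- **Same sections:** summarize all Ad5-nCoV-IH recipients (about 10,210) descriptively with exact 95% CIs, overall and by age group, with no test against ICV.

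The cost is wording in the protocol, carried into the SAP, plus the precision shown above: a standard error of 3.9 rather than 2.8 points at a 20% rate. At the earlier study's 14-day solicited rates in section 3.4.2 (18.57% low-dose inhaled, 38.57% inactivated), 210 per arm still gives 99.6% power. If the ICV rate were only 28% or 25% (assumed), power would be 63% or 36%, against 91% or 64% for the pooled comparison, whose extra power comes from non-randomized subjects.
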